5.1.1. EM Patients

Figure CGAP.5.1 illustrates the study design for EM patients. A major part of this study is a roll over study from parental Study I5Q-JE-CGAN (CGAN) for EM patients who complete Study Period III in Study CGAN, and are willing to continue the study.

The end-of-treatment phase of Study CGAN (Visit 12 of Study CGAN) is equal to the Visit 3 of Study CGAP. The beginning of Study CGAP for EM patients is Visit 3, not Visit 1; Visit 3 is the first injection visit for both EM patients and CM patients in Study CGAP.

All visits except Visit 3 in Study Periods III and IV, patients will use a paper-based headache diary (paper diary) provided by the sponsor, which can take information of the frequency of headaches, migraine headaches, and medication for migraine or headache. Investigators are responsible for data integrity of the paper diary.

At Visit 3, ePRO (electronic Patient-Reported Outcomes) diary will be used as Visit 12 of Study CGAN. It is used to record information of the frequency of headaches, migraine headaches, and medication for migraine or headache.

Abbreviation: SP = study period.

^aPatients who roll over from Study CGAN will start at Visit 3.

^bPatients assigned to 120 mg arm who are from placebo arm in Study CGAN have 240 mg loading dose at Visit 3 and who are from 120 mg (+ 240 mg loading dose) arm in Study CGAN have no 240 mg loading dose but have one 120 mg dose and one placebo dose at Visit 3.

[figure not shown]
Note: The Visit 3 injections are under blind condition for all patients. From Visit 5, patients receive either one 120 mg injection (120 mg arm) or two 120 mg injections (240mg arm) without blinding.

Figure CGAP.5.1. Study I5Q-JE-CGAP protocol design for EM patients.

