5.3. Randomization and Treatment Assignment

5.3.1. EM Patients

There will be 2 treatment arms; galcanezumab 120 mg/month, and galcanezumab 240 mg/month. The patients will be randomized in a 1:1 ratio to receive 120 mg/month of galcanezumab, or 240 mg/month of galcanezumab at Visit 3 of Study CGAN for the patients who roll over from Study CGAN. Patients who were in the galcanezumab treatment arms for Study CGAN continue with the same dose in Study CGAP, while patients who were in the placebo arm in Study CGAN are randomized to 120 mg or 240 mg at Visit 3 of Study CGAN

(randomization ratio = 1:1). If patients who roll over from Study CGAN are confirmed eligible, the patients will begin a 12-month treatment period (Study Period III).

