For EM patients' analysis, baseline is Study CGAP Visit 3 (Study CGAN Visit 12) assessment, unless otherwise specified with some exception (e.g., immunogenicity analysis). If baseline data is not available at Study CGAP Visit 3 (e.g., height), then baseline assessment of CGAN will be used.

Additional exploratory analyses of the data will be conducted as deemed appropriate.

Statistical analysis of this study will be the responsibility of Eli Lilly and Company or designee. SAS[®] software will be used to perform most or all statistical analyses.

Post-Treatment Emergent and Follow-up Emergent are used interchangeably in this study.

Summary tables will display each arm (EM120, EM240, CM120, CM240). In addition, if the summary is sorted by total (LY_ALL), then the "LY_ALL" will be shown (e.g. summary of TEAE, summary of pre-existing condition).

The measurements of PGI-I, PGI-S, MSQ, MIDAS PSMQ-M, or HCRU will be used if they are taken on the same day of the injection date even if the measurements are after injection timing. But if it is after the injection day, then it will be excluded.

For PGI-I, PGI-S, MSQ, MIDAS, and MHD related analysis with repeated measurement in SP III (continuous and binary outcomes), "overall (month 1-12)" will be shown for treatment comparisons at the final DBL.

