5.5.1.4. Baseline and Post-Baseline Definition

[Table CGAP. 5.4](#) describes the rules for determining the patient population and baseline and post-baseline observations for each study phase and type of analysis. When “last of Visit x-x” is used in the table, the last nonmissing observation obtained in the visit interval will be used.

Table CGAP. 5.4 Patient Population with Baseline and Post-Baseline Definitions by Study Period and Type of Analysis

Study Period/Analysis	Patient Population	Baseline Observation	Post-baseline Observation(s)
Study Period III			
Efficacy analyses	ITT Population with a baseline and at least 1 post-baseline observation	Visit 3	All Visits 3.01–16
Mean change from baseline in the number of migraine headache days	PPS Population with a baseline and at least 1 post-baseline observation	Visit 3	All Visits 3.01–16
Quality of Life analyses	ITT Population with a baseline and at least 1 post-baseline observation	Visit 3	All Visits 3.01–16
TEAEs	Safety Population	EM: CGAN Visit 1 – CGAP Visit 3 CM: All Visits 1–3. Pre-existing condition that is still ongoing at Visit 1 should be evaluated as baseline values.	All Visits 3.01–16
Serious Adverse Events, Discontinuations due to Adverse Events	Safety Population	NA	All Visits 3.01–16
C-SSRS categorical analyses	Safety population with a baseline and at least 1 post-baseline C-SSRS assessment	EM: Recent History: CGAP Visit 3 All Prior History: All CGAN Visits 1-12 including lifetime ^a CM: Recent History: All CGAP Visits 1–3 excluding lifetime ^a	All Visits 3.01–16

Study Period/Analysis	Patient Population	Baseline Observation	Post-baseline Observation(s)
		All Prior History: All CGAP Visits 1 – 3 including lifetime ^a	
C-SSRS categorical analyses for improvement	Safety population with a baseline and at least 1 post-baseline C-SSRS assessment	EM: Visit 3 CM: Last of CGAP Visit 1-3.	Last of 3.01–16
Treatment emergent abnormal laboratory values	Safety Population with normal laboratory values at all nonmissing baseline visits (with respect to direction being analyzed) and who have at least 1 post-baseline observation	EM: Visit 3 CM: All Visits 1–3	All Visits 3.01–16
Treatment emergent immunogenicity	Safety Population. ADA follow-up cohort (See Section 5.5.12.1.6)	EM (LY120/LY120, LY240/LY240): CGAN Visit 3 EM (PLA/LY120, PLA/LY240): CGAP Visit 3 CM: Visit 3	All Visits 3.01–16

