Treatment emergent changes in vital signs, weight, and ECGs	Safety Population with a baseline and at least 1 post-baseline observation	EM: Visit 3 CM: Low: Minimum value from Visits 1–3 High: Maximum value from Visits 1–3	Low: Minimum value from Visits 3.01–16 High: Maximum value from Visits 3.01–16
Continuous safety analyses	Safety Population with a baseline and at least 1 post-baseline observation	EM: Visit 3 CM: Last of Visits 1–3	Scheduled visits: 3 < Visits ≤ 16
Study Period III and IV combined			
Efficacy analyses	ITT Population with a baseline and at least 1 post-baseline observation	Visit 3	All Visits 3.01-18
Quality of Life analyses	ITT Population with a baseline and at least 1 post-baseline observation	Visit 3	All Visits 3.01-18

Study Period/Analysis	Patient Population	Baseline Observation	Post-baseline Observation(s)
Continuous safety analyses	Safety Population with a baseline and at least 1 post-baseline observation	EM: Visit 3 CM: Last of Visit 1- 3	All Visits 3.01-18
Treatment emergent immunogenicity	ADA follow-up cohort (See Section 5.5.12.1.6)	EM (LY120/LY120, LY240/LY240): CGAN Visit 3 EM (PLA/LY120, PLA/LY240): CGAP Visit 3 CM: Visit 3	All Visits 3.01–18
Study Period IV			
Continuous safety analyses – change from baseline to LOCF endpoint (ANCOVA)	Post-treatment Population with a baseline and at least one post-baseline observation	EM: Last of Visits 3-16 CM: Last of Visits 1-16	Last Visit: 16.01-18
FEAEs	Post-treatment Population	EM: All Visits in CGAN Visit 1 - 16. CM: All Visits 1- 16. Pre-existing condition that is still ongoing at Visit 1 should be evaluated as baseline values.	All Visits 16.01–18
Serious Adverse Events, Discontinuations due to Adverse Events	Post-treatment Population	NA	All Visits 16.01–18
Follow-up emergent abnormal laboratory values	Post-treatment Population with normal laboratory values at all nonmissing baseline visits (with respect to direction being analyzed) and who have at least 1 post-baseline observation	EM: All Visits 3- 16 CM: All Visits 1- 16	All Visits 16.01–18
Follow-up emergent changes in vital signs, weight and ECGs	Post-treatment Population with a baseline and at least 1 post-baseline observation	EM: Low: Minimum value from Visits 3–16 High: Maximum value	Low: Minimum value from Visits 16.01–18 High: Maximum value from Visits 16.01–18

Study Period/Analysis	Patient Population	Baseline Observation	Post-baseline Observation(s)

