5.5.4. Patient Characteristics

For baseline patient characteristics summary, treatment groups are based on

[Group 1] EM120, EM240, CM120, CM240

[Group 2] LY120/LY120, LY240/LY240, PLA/LY120, PLA/LY240

[Group 3] EM_ALL, CM_ALL, LY_ALL

Hence, each summary will be created for these three groups.

If statistical comparisons are conducted, then following arm will be compared:

Group1: EM120 vs EM240, CM120 vs CM240.

Group2: None.

Group3: EM_ALL vs CM_ALL

Note that source of patient characteristics at baseline for EM patients are defined in the CGAP Protocol Section 2, Schedule of Activities, unless otherwise specified. For example, height is from CGAN Visit 3, and age is from CGAP Visit 3.

The following patient characteristics at baseline will be summarized

- Demographic (age, gender, race and subrace, height, weight, body mass index, Age [<20 , ≥ 20])

Note: body weight (as well as BMI) is based on the last observation before Visit 3 injection.

- Baseline MHD category per 30 day (<8, >=8) (EM: CGAN Month 6. CM: Visit 2 to Visit 3)
- Years since migraine diagnosis (EM: CGAP Visti3. CM: Visit 3)
- Migraine and headache related measures (EM: CGAN Month 6. CM: Visit 2 to Visit 3).
 - number of migraine headache days
 - number of migraine headache days with abortive (acute) medication use
 - number of migraine headache days or headache days with abortive (acute) medication use
 - number of headache days
- PGI-S (EM: CGAN Month 6. CM: Visit 3)
- MIDAS (total, each question) (EM: CGAN Month 6. CM: Visit 3)
- MSQ (total, 3 subscores) (EM: CGAN Month 6. CM: Visit 3)
- Previous migraine prevention treatment (Yes, No, Yes and did not fail, Yes and fail >=1, Yes and fail >=2) (EM: CGAN Visit 1, CM: Visit 1)
- Number of previous migraine prevention treatment fail (EM: CGAN Visit 1, CM: Visit 1)
- Past usage (yes/no) or current usage (yes/no) of followings: Alcohol, caffeine, nicotine replacement therapy, and tobacco and nicotine combined. (EM: CGAN Visit 1, CM: Visit 1)

Note: Except caffeine, summaries are based on patients with ≥ 20 years old.

- Medical history except primary medical conditions (at ICF). Medical history is defined as illness (es) that ended prior to the signing of informed consent (EM: CGAP Visit 3, CM: Visit 1). It will be summarized by preferred term (PT).
- Pre-existing condition (at ICF). Pre-existing conditions are those AEs existing at the study entry. It will be summarized by preferred term (PT) (EM: CGAP Visit 3, CM: Visit 1)

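### The laboratory, vital-sign, weight and ECG baseline is on-drug for LY/LY patients and pre-drug for PLA/LY patients, and each EM arm pools the two

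*SAP*

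**What the plan says.** The general rule in SAP section 5.5.1 is: "For EM patients' analysis, baseline is Study CGAP Visit 3 (Study CGAN Visit 12) assessment, unless otherwise specified". Section 5.1.1 explains what that visit is: "The end-of-treatment phase of Study CGAN (Visit 12 of Study CGAN) is equal to the Visit 3 of Study CGAP". Section 5.3.1 adds: "Patients who were in the galcanezumab treatment arms for Study CGAN continue with the same dose in Study CGAP".

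Table CGAP. 5.4 applies the rule to safety in Study Period III. The laboratory row reads "EM: Visit 3 CM: All Visits 1–3", and its population is "Safety Population with normal laboratory values at all nonmissing baseline visits (with respect to direction being analyzed". The row headed "Treatment emergent changes in vital signs, weight, and ECGs" and the continuous safety row also give Visit 3 for EM patients. The continuous safety row for Study Periods III and IV combined does the same, as does section 5.5.12.1.4 for qualitative ECG.

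One row of the table differs. For treatment-emergent immunogenicity it has "EM (LY120/LY120, LY240/LY240): CGAN Visit 3", and it gives PLA/LY120 and PLA/LY240 CGAP Visit 3.

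Section 5.5.12 displays safety by four arms (EM120, EM240, CM120, CM240) unless stated otherwise.

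**The concern.** These measures belong to the primary objective, long-term safety and tolerability (SAP Table CGAP. 4.1). The LY/LY patients have the longest exposure in the study, and their baseline is read after about six months on drug. The PLA/LY patients in the same column are measured from a drug-free value. A reader of an EM120 or EM240 table would naturally take a treatment-emergent abnormality, or a change from baseline, as relative to the untreated state. That holds for PLA/LY but not for LY/LY. At stake is whether the safety tables show cumulative change since first dose in the patients best placed to reveal it, and whether each EM column has a single meaning.

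**Working it through.** The plan attaches no figure to this definition, so there is none to reproduce. The check traces the baseline through the SAP and then applies the SAP's own criteria.

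**Step 1. What the baseline is, by group**
- LY/LY: first injection at CGAN Visit 3 (section 5.5.8), same dose continued (section 5.3.1), baseline at CGAP Visit 3. The prior exposure is about six months, because section 5.5.4 takes the EM baseline diary data from the last CGAN month: "Migraine and headache related measures (EM: CGAN Month 6. CM: Visit 2 to Visit 3". The value is on-drug.
- PLA/LY: placebo in CGAN, first galcanezumab at CGAP Visit 3. The value is pre-drug.
- EM120 and EM240 each contain both groups (section 5.5.1).

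**Step 2. What each analysis does with a shift still present at CGAP Visit 3**
- Laboratory low/high/abnormal (section 5.5.12.1.5): a patient already abnormal in that direction leaves the at-risk set.
- ECG low/high (section 5.5.12.1.4): the same. The two baseline-normal qualitative ECG populations also lose the patient.
- Vital signs and weight (Table CGAP. 5.6): the all-patient rows drop nobody, but the criteria need a change from baseline, so the earlier shift is absorbed. In the subsets defined by baseline category, the patient may fall in a different subset.
- QTc increase and continuous measures: nobody is dropped; the shift is absorbed.

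**Step 3. Illustration with the SAP's thresholds.** The patient values are assumed and show only how the rule works.

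| Measure and criterion | Pre-drug | CGAP Visit 3 | Later | Change from pre-drug | Change from Visit 3 |
|---|---|---|---|---|---|
| Systolic BP: ≥140 and rise ≥20 | 124 | 136 | 146 | 146 − 124 = 22, counted | 146 − 136 = 10, not counted |
| Diastolic BP: ≥90 and rise ≥10 | 78 | 86 | 92 | 92 − 78 = 14, counted | 92 − 86 = 6, not counted |
| Weight: gain ≥7% | 60 kg | 63 kg | 65 kg | 65/60 − 1 = 8.3%, counted | 65/63 − 1 = 3.2%, not counted |
| QTcF: increase >30 msec | 405 | 428 | 440 | 440 − 405 = 35, counted | 440 − 428 = 12, not counted |

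**Step 4. How many patients could leave a laboratory at-risk set.** Section 5.2.1 plans 120 EM patients per arm. The documents do not give the LY/LY share or the frequency of abnormalities, so both are assumed. With a share of 40% to 67%, LY/LY number 48 to 80 per arm. If 2%, 5% or 10% of them have a CGAN-onset abnormality in a given test at CGAP Visit 3, then 48 to 80 times that proportion leave:
- 2%: 1.0 to 1.6 patients per EM arm
- 5%: 2.4 to 4.0
- 10%: 4.8 to 8.0

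These figures give a sense of scale only; they are not an estimate for this trial.

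**The case against.** The strongest defence is that the SAP asks a consistent and legitimate question: what emerges during CGAP. The primary objective refers to one year of treatment. The TEAE baseline runs from CGAN Visit 1 to CGAP Visit 3, and the C-SSRS history baselines include CGAP Visit 3 or CGAN Visits 1 to 12, so those rows also count on-drug CGAN findings as baseline. Section 5.5.1 names immunogenicity as an example of an exception. CGAN had its own double-blind period with a placebo arm, in which the first six months can be reported.

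Much of this stands. Emergence since CGAP entry should be kept. The TEAE and C-SSRS rows show that CGAN data are available, but they are no precedent for a pre-drug baseline; only the immunogenicity row is.

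Two provisions also mitigate. The ALT, AST, ALP and bilirubin multiples of the upper limit cover all patients with a post-baseline value, so an elevation that persists at those levels is still counted. The listings of abnormal laboratory and hepatic results are by six arms under section 5.5.1, so LY/LY patients can be seen there.

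The defence does not make one label mean the same thing for LY/LY and PLA/LY, and it does not provide change since first dose for LY/LY.

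A reader might infer more than the documents support:
- That every LY/LY patient who was ever abnormal in CGAN is lost. The EM baseline is a single visit, so an abnormality that had resolved by then leaves the patient at risk.
- That risk is understated because cumulative incidence over 18 months exceeds incidence over 12. That compares windows of different length. If the onset rate were constant, LY/LY patients still at risk and PLA/LY patients would have the same 12-month risk, and pooling them would not distort it. Mixing matters when the rate depends on time on drug or when change accumulates.
- That early shifts go unreported. The CGAN plan and the main protocol are not among the documents, so this cannot be shown.

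**Conclusion.** The point holds as one of definition and display. For laboratory values, vital signs, weight, ECG and continuous safety measures in Study Period III, and for the continuous measures also in Study Periods III and IV combined, the EM baseline is on-drug for LY/LY and pre-drug for PLA/LY, and the main tables pool the two. For LY/LY these tables report emergence since CGAP entry only. Exclusion of patients is confined to the laboratory and ECG low/high sets and the baseline-normal qualitative ECG sets; elsewhere the effect is absorption into baseline.

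The size cannot be derived. It depends on the CGAN allocation, on how often shifts occurred in CGAN and on whether they persisted to CGAP Visit 3, none of which is given. The conclusion rests only on the SAP's definitions. It supports an inexpensive addition, not replacement of the main baseline.

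**What to change.** 1. Keep the CGAP Visit 3 analysis as planned, and label the LY/LY baseline as on-drug.
2. Show the laboratory, vital-sign, weight and ECG summaries by the six arms already used for immunogenicity and for selected TEAE tables.
3. Add a supplementary analysis to Table CGAP. 5.4 and section 5.5.12.1.4: baseline at CGAN Visit 3, before the first dose, for LY120/LY120 and LY240/LY240, and at CGAP Visit 3 for PLA/LY. The CGAN schedule is not supplied, so confirm which of these tests were taken at CGAN Visit 3.
4. State whether CGAN on-treatment visits count as post-baseline in that analysis. If the window stays at Visits 3.01 to 16, only shifts that persist or recur after CGAP Visit 3 are recovered.

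The cost is extra tables and the merging of CGAN baseline values; CGAN data already feed the adverse-event, C-SSRS and immunogenicity baselines. The drawback is unequal time since baseline: at CGAP Month 12, LY/LY would be about 6 + 12 = 18 months from baseline and PLA/LY 12 months. In the supplementary analysis the two should therefore be read side by side, not pooled.

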Abbreviations: CGRP = Calcitonin-gene related peptide; CRP = Lilly Clinical Research Physician; CRS = Lilly Clinical Research Scientist; C-SSRS = Columbia Suicide Severity Rating Scale; D14 = Day 14; DNA = deoxyribonucleic acid; ECG = electrocardiogram; ET = early termination; FSH = follicle stimulating hormone; HbA1c = glycated haemoglobin; HCRU = Health Care Resource Utilization; MIDAS = Migraine Disability Assessment test; MSQ (v2.1) = Migraine Specific Quality of Life Questionnaire; PGI-I = Patient Global Impression of Improvement; PGI-S = Patient Global Impression of Severity; PK = pharmacokinetics; PSMQ-M = Participant Satisfaction with Medication Questionnaire-Modified; RNA = ribonucleic acid; SP = Study Period; SHSF = Self-harm supplement form; SHFU = Self-harm follow-up form.

Note: Selected tests may be obtained in the event of a treatment-emergent hepatic abnormality and follow-up may be required with patients in consultation with the Lilly, or its designee (CRP/CRS). See Appendix 4 of the protocol for more details regarding specific hepatic monitoring tests. If the patient has discontinued the trial and returns for hepatic follow-up, the site should use the 800 series as the visit designation.

- ^a The eligibility period of the prospective baseline assessment will last from 30 to 40 days. Investigators and patients may have up to an additional 5 days to schedule their Visit 3 appointment (beyond the 40 days); however, eligibility will be based on the 30-40 day period.
- b Physical examinations at screening must include a neurological exam.
- ^c Electrocardiograms as single, 12-lead digital will be performed at Visit 1, Visit 3, Visit 10, Visit 16, and Visit 18 or early termination. Note: The Visit 3 ECG should be collected prior to blood draws and dosing. Patients must be supine for approximately 5 to 10 minutes before ECG collection and remain supine but awake during ECG collection. For screening only, ECG results will be read locally.
- Vital signs will include body temperature, blood pressure, and pulse. Blood pressure and pulse will be measured in triplicate in the sitting position and should be measured prior to blood draws. Blood pressure will be assessed by utilizing a calibrated machine.

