5.4. Scientific Rationale for Study Design

The length of the open-label treatment of galcanezumab for 1 year is considered sufficient to assess the consistent effectiveness and safety on the patients with CM in comparison to those on the patients with EM. A 4-month post-treatment follow-up phase is included to evaluate patient safety during wash-out of galcanezumab. This allows for a total of 5 months of observation from the time of last injection of galcanezumab. A 5-month post-treatment observation period allows for a wash-out of approximately 5 elimination half-lives of galcanezumab and should decrease galcanezumab serum concentrations by approximately 97% during this time.

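### Treatment-emergent vital-sign and ECG changes use a single baseline reading in EM but the extreme of Visits 1–3 in CM, so EM and CM rates in the same table are not comparable

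*SAP*

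**What the plan says.** SAP Section 5.5.1.4, Table CGAP. 5.4, Study Period III row for treatment-emergent changes in vital signs, weight and ECGs, gives the baseline as "EM: Visit 3 CM: Low: Minimum value from Visits 1–3 High: Maximum value from Visits 1–3". The post-baseline value is the same for both populations: "Low: Minimum value from Visits 3.01–16 High: Maximum value from Visits 3.01–16". The criteria in Tables CGAP. 5.6 and 5.7 are also common to both.

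The number of CM baseline readings follows from the protocol addendum, Section 2 (Schedule of Activities):

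- **Vital signs.** The footnote reads "Vital signs will include body temperature, blood pressure, and pulse". The schedule marks Visits 1 and 3 before dosing, then Visits 5–10, 13 and 16 in Study Period III.
- **ECG.** "Electrocardiograms as single, 12-lead digital will be performed at Visit 1, Visit 3, Visit 10, Visit 16, and Visit 18 or early termination". The same footnote adds: "For screening only, ECG results will be read locally".
- **Weight.** Visit 1 is the only scheduled pre-dose value. SAP Section 5.5.4 is consistent with that: "Note: body weight (as well as BMI) is based on the last observation before Visit 3 injection".

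Safety results are displayed by EM120, EM240, CM120 and CM240 (SAP Section 5.5.12). When these four arms are tested, the comparisons are between doses within EM and between doses within CM (SAP Section 5.5.1).

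**The concern.** The maximum of two noisy readings sits, on average, above a single reading, and the minimum sits below it. A criterion that asks for a rise or fall from baseline is therefore harder to meet in CM than in EM, although the threshold printed in the table is identical.

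Vital signs and ECGs are among the primary safety endpoints (SAP Table CGAP. 4.1). The addendum's rationale (Section 5.4) is that a year of treatment suffices to "assess the consistent effectiveness and safety on the patients with CM in comparison to those on the patients with EM". A reader who follows that rationale will compare the CM and EM columns of one table. Part of any difference will come from the baseline definition, and nothing in either document warns of this or gives a reason for it.

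**Working it through.** The documents give no flag rate and no within-patient SD for these measures, so there is no figure of the plan's own to reproduce. The direction follows from the text; the size needs assumptions.

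**Direction.** Let a patient's readings be Y = true level + error, with independent normal errors of visit-to-visit SD s. Then

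E[max(Y1, Y3)] − E[Y3] = s/√π = 0.564 s.

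For s = 7 this is 0.564 × 7 = 3.9 mm Hg; for s = 9 it is 0.564 × 9 = 5.1 mm Hg. The average CM patient needs that much more to meet the same change criterion. The minimum behaves symmetrically. Averaging the triplicate readings within a visit (SAP Section 5.5.12.1.3) reduces s but does not remove variation between visits.

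**Size.** Simulation of 400,000 patients per scenario, with the same true level, true change and post-baseline visits under both rules:

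- EM flag for SBP high: max(post) ≥ 140 and max(post) − Y3 ≥ 20.
- CM flag: max(post) ≥ 140 and max(post) − max(Y1, Y3) ≥ 20.
- From the documents: criteria; two pre-dose readings in CM; 8 scheduled post-baseline vital-sign visits; 2 post-baseline ECGs in Study Period III (Visits 10 and 16).
- Assumed: SBP mean 118, between-patient SD 11; QTcF mean 410, between-patient SD 18; the values of s shown; and the CM post-baseline schedule for EM too, because the EM schedule is not in the documents.

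SBP ≥ 140 with increase ≥ 20, EM rule against CM rule:

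| True change | s = 7 | ratio | s = 9 | ratio |
|---|---|---|---|---|
| 0 | 2.8% vs 0.9% | 0.32 | 8.2% vs 3.8% | 0.47 |
| +10 mm Hg | 24.2% vs 15.5% | 0.64 | 35.1% vs 25.3% | 0.72 |
| +20 mm Hg | 67.8% vs 61.9% | 0.91 | 73.2% vs 66.7% | 0.91 |

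Widening s to 5–11 gives ratios of 0.13–0.58 with no change, 0.48–0.77 at +10 and 0.91 at +20. Moving the population to mean 116, SD 12 (s = 7–9) gives 0.30–0.48 with no change.

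In a CM arm of 30, the absolute gap is:

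- no change: 30 × (0.0279 − 0.0089) = 0.6 patients at s = 7, and 30 × (0.0815 − 0.0383) = 1.3 at s = 9;
- +10 mm Hg: 30 × (0.2423 − 0.1551) = 2.6 and 30 × (0.3507 − 0.2529) = 2.9.

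Other vital signs behave alike. DBP high (s = 4–8): ratio 0.39–0.73 with no change, 0.92 at +10 mm Hg. Pulse high (s = 5–9): 0.36–0.71 with no change, 0.79–0.88 at +10 beats/min.

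QTcF increase > 30 msec, **if both the Visit 1 and Visit 3 ECGs count**:

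| True change | s = 8 | s = 10 | s = 13 |
|---|---|---|---|
| 0 | 0.10 | 0.16 | 0.27 |
| +10 msec | 0.24 | 0.33 | 0.41 |
| +20 msec | 0.48 | 0.53 | 0.58 |

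If only the Visit 3 ECG is analysed, the ratio is 1.00. Weight is also 1.00, with one scheduled pre-dose value. For PR, QRS and the absolute QTc limits, Table CGAP. 5.7 has no change component, so the rule alters who is eligible (SAP Section 5.5.12.1.4), not how far a patient must move.

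**The case against.** The strongest reply is that no planned test is affected. Both arms in each Fisher comparison share one baseline rule, and no EM-against-CM test of these measures is specified. That stands: a reader might infer that the comparisons are biased, and the documents do not support it.

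Second, the large ratios arise when the true change is nil or small. Much of the gap is chance flags that the CM rule avoids, and with about 30 CM patients per arm the no-change gap is roughly one patient. That also stands. It would be wrong to infer that large true changes are mostly missed in CM: when the true SBP or DBP change equals the criterion, the relative loss is only 8–9%.

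Third, the asymmetry has an origin. EM patients enter this study at Visit 3 (SAP Section 5.1.1), the CM rows use the available pre-dose visits, and in Study Period IV, where EM also has several baseline visits, both populations get the minimum/maximum. This explains the rule but does not make the Study Period III rates comparable. The SAP already uses the last pre-dose value for CM in its continuous safety row and for qualitative ECG findings.

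Fourth, it is tempting to say that the CM ECG baseline mixes local and central readers. The addendum says only that screening ECGs are read locally; neither document says whether that reading enters the analysis.

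Fifth, one might extend the point to the laboratory row, "EM: Visit 3 CM: All Visits 1–3". There the rule decides who is at risk, not the change required, and HbA1c has no Visit 1 value in CM. The effect has not been quantified and is not claimed here.

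**Conclusion.** The point holds as one of comparability between populations. For the same true course, the Study Period III rule flags CM patients less often than EM patients. With an assumed s of 7–9 mm Hg, the SBP ratio is about 0.3–0.5 with no true change, 0.6–0.7 at +10 mm Hg and 0.9 at +20. For a QTcF increase above 30 msec it is about 0.1–0.6, conditional on the Visit 1 ECG being analysed. The direction needs no particular SD; the sizes rest on assumed SDs, normal errors and equal post-baseline visits. Unscheduled pre-dose readings in CM would widen the gap.

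A reader might conclude that CM will look safer by definition alone. That goes too far: patients continuing galcanezumab from Study CGAN are already on drug at EM Visit 3, so the two populations differ at baseline in other ways, and the net direction of an EM/CM difference cannot be read off this rule alone.

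**What to change.** Add to the SAP one CM table of treatment-emergent vital-sign and ECG changes for Study Period III with Visit 3 (the last pre-dose value) as baseline, and name it as the table for any reading of CM beside EM. Keep the minimum/maximum table for the CM120 against CM240 comparison, with a footnote that its rates are not comparable with EM. State whether the Visit 1 ECG is in the analysis dataset, and do not use the locally read tracing in the quantitative baseline when a Visit 3 ECG exists. Weight needs no change.

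The cost is one extra derivation and one footnote. The Visit 3 table will show more chance flags in CM than the minimum/maximum table, as EM already does. Adding a table rather than replacing one suits the timing: SAP Version 3 was written after interim results had been reviewed (Section 5.5), and treatment-emergent ECG tables were interim outputs (Section 5.8.1). With a common rule the ratio is 1.00 by construction for the same true course. This removes one source of non-comparability and leaves the prior-exposure difference in EM untouched.
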